5.4 Definition of Dose-Limiting Toxicity

Toxicities will be graded in severity according to the guidelines outlined in the NCI-CTCAE version 4.0. Dose limiting CNS and non-CNS (hematologic and non-hematologic) toxicities will be defined differently and will be based on events that occur during the study period. In order to be declared as dose-limiting toxicity, an adverse event must be related (definite, probable, or possible) to study treatment.

A dose-limiting toxicity (DLT) will be defined as any one of the following adverse events occurring within 8 weeks from last dose of radiation therapy:

CNS toxicities:

Acute CNS toxicities (occurring \leq 30 days after completing FSRT treatment):

• Any grade 3 or higher central nervous adverse events including but not limited to headache, dizziness, vertigo, new onset seizures, cerebral edema, cerebral hemorrhage, and new onset neurologic deficit.

Delayed onset CNS toxicities (occurring >30 days after completing FSRT treatment):

 Any grade 3 or 4 adverse event arising within the irradiated volume including but not limited to radiation necrosis or focal neurological deficits.

Non-CNS toxicities:

Non-hematologic toxicities:

- Any grade 3 or higher non-hematologic adverse event with the exception of alopecia, fatigue, and anorexia.
- Grade 3 or higher nausea and/or vomiting that persists ≥ 48 hours despite optimal medical management.

Hematologic toxicities:

- Grade 4 neutropenia lasting for \geq 7 days in duration
- Grade \geq 3 febrile neutropenia with/without infection

• Grade 4 thrombocytopenia

Dose escalation will be determined based on the occurrence of DLTs. For the purposes of determining whether to advance the dose levels, DLTs will be counted by patient. In the event of the development of any grade 3 or 4 toxicity felt to be at least possibly related to study drug, TPI 287 will be held until resolution to grade 1 or baseline assuming that occurs within 15 day window.

Dose escalation will follow the standard 3+3 design. The enrollment to next higher dose level will be delayed for 8 weeks after the completion of FSRT by the last patient enrolled at the dose level. This period of 8 weeks will allow monitoring potential delayed toxicities. Management and dose modifications associated with the above adverse events are outlined in Section 6. Dose escalation will proceed according to the following scheme. Dose-limiting toxicity (DLT) is defined above.

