5.5 General Concomitant Medication and Supportive Care Guidelines

Because there is a potential for interaction of TPI 287 with other concomitantly administered drugs through the cytochrome P450 system, the use of drugs or herbal supplements that are known to be strong inhibitors/inducers of CYP3A4 and CYP2C8 are not permitted (Appendix B).

Prophylactic use of corticosteroids is allowed during the study to limit symptoms from metastases or radiation.

Non-enzyme inducing anti-epileptic drugs may be utilized to control or prevent seizures.

Principal Investigator should be alerted if the patient is taking any agent known to affect or with the potential to affect selected CYP450 isoenzymes.

5.6 **Duration of Therapy**

Patients will receive TPI 287 on days 1, 8, and 15 (total of 3 doses). On day 1, the TPI 287 will be administered 4 (+/-2) hours prior to FSRT.

5.7 **Duration of Follow Up**

Patients will be seen in follow-up on the 3rd, 6th, 9th, 12th, 15th, and 18th month following the first day of treatment with TPI 287. Patients will be followed for 18 months after first treatment on study or until death, whichever occurs first.

The following will be obtained at pre-treatment evaluation and at each follow up visit: Symptoms history, vital signs/ height and weight, physical examination, KPS/ECOG score, Mini-Mental State Examination, steroid use, quality of life questionnaire, and toxicity evaluation.

Radiologic assessment, MRI brain with and without gadolinium, will be performed at pretreatment and every three months following the end of treatment until the patient is off-study or reaches the 18 month study completion date.

Furthermore, the principal investigator will have close collaboration with oncologists treating the systemic malignancy. Information regarding the status of systemic malignancy such as results of standard imaging evaluations, serum biomarkers measurements, and systemic treatments will be collected and recorded at each visit.

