6. DOSING DELAYS/DOSE MODIFICATIONS/TREATMENT DISCONTINUATION

Dose Level	TPI 287 Dose
-2	$5 \text{ mg/m}^2/\text{dose}$
-1	$7 \text{ mg/m}^2/\text{dose}$
1	14 mg/m ² /dose
2	28 mg/m ² /dose
3	56 mg/m ² /dose
4	85 mg/m ² /dose
5	113 mg/m ² /dose
6	$127.5 \text{ mg/m}^2/\text{dose}$

Table 3. Dose Levels for Dose Modification of TPI 287

Below are dose modification tables for the following adverse events: nausea, vomiting, diarrhea, neutropenia, and thrombocytopenia:

Table 4. Management of Nausea

Nausea	Management/Next Dose for TPI 287
\leq Grade 1	No change in dose
Grade 2	Hold until \leq Grade 1. Resume at same dose level.
Grade 3	Hold [*] until < Grade 2. Resume at one dose level lower, if indicated. [*]
Grade 4	Off protocol therapy
*Patients requiring a delay of ≥ 2 weeks should go off protocol therapy.	
Recommended management: antiemetics.	

Vomiting	Management/Next Dose for TPI 287	
\leq Grade 1	No change in dose	
Grade 2	Hold until \leq Grade 1. Resume at same dose level.	
Grade 3	Hold [*] until < Grade 2. Resume at one dose level lower, if indicated.	
Grade 4	Off protocol therapy	
*Patients requiring a delay of >2 weeks should go off protocol therapy.		
Recommended management: antiemetics.		

Table 5. Management of Vomiting

Table 6. Management of Diarrhea

Diarrhea	Management/Next Dose for TPI 287	
\leq Grade 1	No change in dose	
Grade 2	Hold until \leq Grade 1. Resume at same dose level.	
Grade 3	Hold [*] until < Grade 2. Resume at one dose level lower, if indicated. [*]	
Grade 4	Off protocol therapy	
*Patients requiring a delay of >2 weeks should go off protocol therapy.		
Recommended management: Loperamide antidiarrheal therapy		
Dosage schedule: 4 mg at first onset, followed by 2 mg with each loose motion until diarrhea-		
free for 12 hours (maximum dosage: 16 mg/24 hours)		
Adjunct anti-diarrheal therapy is permitted and should be recorded when used.		

Table 7. Management of Neutropenia

Neutropenia	Management/Next Dose for TPI 287			
≤ Grade 1	No change in dose			
Grade 2	Hold until \leq Grade 1. Resume at same dose level.			
Grade 3	Hold [*] until < Grade 2. Resume at one dose level lower, if indicated.			
Grade 4	Off protocol therapy			
*Patients requiring a delay of >2 weeks should go off protocol therapy.				
Table 8. Management of Thrombocytopenia				
Thrombocytopenia	nia Management/Next Dose for TPI 287			
\leq Grade 1	No change in dose			
Grade 2	Hold until \leq Grade 1. Resume at same dose level.			

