10. STUDY CALENDAR

Baseline evaluations are to be conducted within 1 week prior to start of protocol therapy. MRI scans must be done ≤ 2 weeks prior to the start of therapy. In the event that the patient's condition is deteriorating, laboratory evaluations should be repeated within 48 hours prior to initiation of the next cycle of therapy.

	Baseline Concurrent phase		Single agent phase		Final [†]	Follow up ^g
		D1	D8	D15		
TPI-287 infusion		Х	Х	Х		
XRT ^a		Х				
Informed Consent	X					
History and Con-meds	Х	х	Х	Х	Х	Х
Baseline Symptoms ^b	X					
Performance status (Karnofsky performance status/ECOG)	Х	Х	Х	Х	Х	Х
Physical Examination (including neurological assessment)	Х	Х	Х	Х	Х	Х
Vital signs and Height/Weight	X	Х	Х	Х	Х	Х
Documenting status of systemic disease	X	X	Х	Х	Х	X
Adverse event evaluation		Х	Х	Х	Х	Х
Quality of life assessment (QLQ-BN20 and QLQ-C15-PAL)	X	X	Х	Х	Х	X
Steroid use assessment	Х	Х	X	Х	X	Х
Blood ^c	Х	Х	Х	Х	Х	
B-HCG	Х					
Radiological assessment ^d	Х					Х
PK samples ^e			X			
Mini-Mental State Examination	Х	Х	Х	Х	Х	X
Lumbar puncture			Х			

^a Radiotherapy will be delivered once daily Monday through Friday, D1-5 for a total of 5 treatments.

^b Baseline symptoms include symptoms occurring on D1 prior to receiving TPI 287 and within 1 week prior.

^c Blood will include CBC and differential, sodium, potassium, chloride, creatinine, AST, ALT, bilirubin, ALP, albumin, calcium, magnesium, phosphate.

^d Radiologic assessment, MRI brain with and without gadolinium, will be performed at pre-treatment and every three months following the end of treatment until the patient is off-study or reaches the 18 month study completion date.

^e PK samples (blood and CSF) will be collected on D8.

^fA final visit will be performed approximately 30 days following completion of treatment with FSRT and/or TPI-287 (whichever treatment occurs last).

^g Information pertaining to survival and long term assessment of the subject's disease status and adverse events will be collected approximately every 12 weeks beginning after the final visit for period of up to 18 months.

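### The DLT window and the wait before the next dose level both end 8 weeks after FSRT and do not move when TPI 287 is held, so two long holds can leave about 18 days of post-drug observation

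*Combined protocol and SAP*

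**What the plan says.** Section 5.4 defines a DLT as a listed, treatment-related event "occurring within 8 weeks from last dose of radiation therapy". The same section sets the wait between levels: "The enrollment to next higher dose level will be delayed for 8 weeks after the completion of FSRT by the last patient enrolled" at the current level. Neither rule refers to the last dose of TPI 287.

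Footnote a of the Study Calendar (Section 10) fixes the radiation days: "Radiotherapy will be delivered once daily Monday through Friday, D1-5 for a total of 5 treatments". Section 5.6 plans TPI 287 on days 1, 8 and 15, so two of the three doses come after radiation has ended.

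Doses can be held, and the limits on a hold differ by place:

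- For related grade 3 or 4 toxicity, Section 5.4 says "TPI 287 will be held until resolution to grade 1 or baseline assuming that occurs within 15 day window".
- The footnotes to Tables 5 to 8 in Section 6 say "Patients requiring a delay of >2 weeks should go off protocol therapy".
- The footnote to Table 4 (nausea) ends therapy at a delay of two weeks or more.
- In these tables the footnote mark sits on the grade 3 rows only. Grade 2 holds therefore carry no explicit limit.

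The final visit is timed differently. Under footnote f of the Study Calendar, a "final visit will be performed approximately 30 days following completion of treatment with FSRT and/or TPI-287", whichever ends last.

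**The concern.** Radiation is the same at every level. TPI 287 is what is escalated, and the MTD is defined for it. Both observation limits are nevertheless tied to the fixed component, so each day that TPI 287 is delayed is a day lost from observation after the last dose. Holds are triggered by toxicity, so the patients who lose observation are those already showing some.

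After the third dose, the next scheduled adverse event evaluation and blood count in the Study Calendar is the final visit. The month 3 follow-up comes later and has no scheduled blood count. If the final visit falls after day 61, a patient can be counted as DLT-free, and the next level can open, before any scheduled assessment after the last dose. Three of the DLT criteria are hematologic and depend on blood counts.

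The escalation rules are sensitive to a single event. In a cohort of three, one missed DLT turns 1 of 3 (add three patients) into 0 of 3 (escalate), and levels 1 to 3 double each time (14, 28, 56 mg/m²).

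**Working it through.** The plan states no post-drug observation period, so there is no figure to reproduce. The check is calendar arithmetic.

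**Inputs**
- Last FSRT fraction: day 5 (Study Calendar, footnote a).
- DLT window and wait before the next level: 8 weeks = 56 days after that (Section 5.4).
- Planned TPI 287: days 1, 8, 15, so a 7-day interval (Section 5.6).
- Longest hold: 14 days (Tables 5 to 8), 13 days (Table 4), 15 days (Section 5.4).
- Final visit: about 30 days after the last treatment (Study Calendar, footnote f).

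**Formulas.** Let h2 and h3 be the holds before doses 2 and 3.
- Window closes: 5 + 56 = day 61.
- Last TPI 287 day: L = 1 + (7 + h2) + (7 + h3) = 15 + h2 + h3.
- Observation after the last dose: 61 − L.
- Final visit: about L + 30.

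| Holds | Last dose (day) | Days to day 61 | Final visit (about day) | Final visit minus day 61 |
|---|---|---|---|---|
| None | 15 | 46 | 45 | −16 |
| One of 14 days | 29 | 32 | 59 | −2 |
| One of 15 days | 30 | 31 | 60 | −1 |
| Two of 13 days | 41 | 20 | 71 | +10 |
| Two of 14 days | 43 | 18 | 73 | +12 |
| Two of 15 days | 45 | 16 | 75 | +14 |

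In the two 14-day case, dose 2 moves from day 8 to day 22, dose 3 would follow on day 29, and it moves to day 43. Compared with no hold, the observation falls by 1 − 18/46 = 61%.

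**Threshold.** Observation drops below 30 days when 61 − (15 + h2 + h3) < 30, that is, when total delay exceeds 16 days. One permitted hold does not reach this; two long ones do.

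**Other readings.** If the two-week limit is cumulative, the minimum is 61 − 29 = 32 days. If a held dose is omitted rather than given late, the last dose is no later than day 15 and at least 46 days remain.

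**Can such a patient be DLT-free so far?** Yes. Section 6 calls for holds at grade 2 nausea, vomiting, diarrhea, neutropenia or thrombocytopenia, and at grade 3 neutropenia or thrombocytopenia. None of these is on the DLT list in Section 5.4, unless the neutropenia is febrile. Section 6 allows one dose reduction per patient but does not limit the number of holds, and a grade 2 hold resumes at the same level.

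**What catches an event after day 61?** The paragraph below Table 2 in Section 5.4 holds escalation for delayed-onset, treatment-related CNS toxicity of grade 3 or higher at any time. It has no counterpart for non-CNS toxicity, such as late hematologic events or peripheral neuropathy (a reported TPI 287 effect, Sections 2.2 and 7.1.2). One sentence in Section 5.9 mentions delayed-onset toxicity of grade 3 or higher without the word CNS. However, Section 5.4 defines delayed onset for CNS events only, and Section 5.9 is a rule for closing the study that does not feed the DLT count.

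**The case against.** The case against giving this much weight is substantial.

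- **It is a stacked worst case.** It takes two long holds, and for the next level to open on that patient's day 61 the patient must be the last enrolled at the level. With no hold or one, the window already exceeds the plan's 30-day post-treatment visit. The documents give no frequency for two holds. All this stands. For a patient enrolled earlier, the next level opens later, but the patient's own DLT window still closes on their own day 61.
- **The 18 days depend on readings the plan does not settle:** late rather than omitted doses, and a limit per hold. The hold-and-resume wording favors both, but neither is stated. Nor is 18 a floor, given the conflicting limits and the unmarked grade 2 rows.
- **Many holds make the window irrelevant.** DLTs are counted by patient. Most related non-hematologic events of grade 3 or higher are DLTs in themselves, and grade 4 events in the Section 6 tables end therapy. After grade 3, a dose may resume one level lower, so a later event says less about the assigned level. This narrows the gap mainly to grade 2 events and to non-febrile grade 3 neutropenia or thrombocytopenia.
- **The radiation anchor is reasoned.** Section 5.4 gives delayed toxicity as the purpose of the 8 weeks. Section 2.2 reports a single-agent weekly MTD of 127.5 mg/m², which is this trial's top level, so the main unknown is the combination. That supports keeping the 8 weeks. It does not explain why a delayed dose leaves them unchanged.
- **There are other safeguards.** Adverse events are captured to the end of participation (Section 7.4), related serious events are reported late as well (Section 7.5), and the Protocol Monitoring Committee reviews monthly and may suspend the study (Section 12.2). Unscheduled counts may also detect events. None of these turns a late non-CNS event into a DLT.

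A reader might go further and infer that held patients routinely get only 18 days, or that the MTD will be materially too high. The documents support neither: one hold leaves 32 days, and nothing allows the number of missed events to be estimated.

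**Conclusion.** The point holds in a limited form. The DLT window and the wait before the next level end on day 61 whatever happens to TPI 287. This falls short of the plan's own 30-day post-drug visit only when total delay exceeds 16 days. With two full 14-day holds, 18 days remain, and the final visit with its blood count comes about 12 days after the window has closed. The range is 16 to 20 days under the other stated limits.

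This assumes that held doses are given late, that dose 3 follows dose 2 by at least 7 days, and that a two-week limit applies to each hold, grade 2 holds included. With a cumulative limit the minimum is 32 days and the shortfall disappears.

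Where the shortfall occurs, late non-CNS drug toxicity can escape the DLT count. The bias is toward too few DLTs; its size is unknown. This is a cheap improvement to the design, not a flaw that undermines it.

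**What to change.** In Section 5.4, end each patient's DLT window at the later of (a) 8 weeks after the last FSRT fraction and (b) the final visit, about 30 days after the last TPI 287 dose. Tie the wait before the next level to the same point. The final visit is already in the Study Calendar; no visit is scheduled at 8 weeks after FSRT, and this change does not need one. It alters no dose, hold or treatment rule.

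Cost: one sentence. With no hold or one, the final visit (about day 45 or day 59) falls before day 61, so there is essentially no delay, though the one-hold margin is only about two days and the visit date is approximate. With two full holds in the last-enrolled patient, the next level opens about 73 − 61 = 12 days later (10 to 14 under the other stated limits).

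Separately, the sponsor should reconcile the hold limits in Section 5.4 and in Tables 4 to 8 of Section 6. It should also state whether a held dose is given late or omitted, whether the limit is per hold or cumulative, and whether it covers grade 2 holds. Those are clinical decisions for the sponsor, but the observation period cannot be fixed exactly until they are settled.

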Number of Patients with DLT at a Given Dose Level	Escalation Decision Rule
0 out of 3	Enter 3 patients at the next dose level.
≥2	Dose escalation will be stopped. This dose level will be declared the maximally administered dose (highest dose administered). Three (3) additional patients will be entered at the next lowest dose level if only 3 patients were treated previously at that dose.
1 out of 3 or ≥ 2 grade 2 CNS toxicities	 Enter at least 3 more patients at this dose level. If 0 of these 3 patients experience DLT, proceed to the next dose level. If 1 or more of this group suffer DLT, then dose escalation is stopped, and this dose is declared the maximally administered dose. Three (3) additional patients will be entered at the next lowest dose level if only 3 patients were treated previously at that dose.
≤1 out of 6 at highest dose level below the maximally administered dose	This is the dose to be used in the expanded cohort and will be considered recommended phase 2 dose. At least 6 patients must be entered at this dose.

Table 2. Dose Escalation Rules

If dose level 1 is found to cause unacceptable toxicity, the dose will be de-escalated to level -1 (7 mg/m^2). Three patients will be enrolled at dose level -1. If no DLT is observed, three additional patients will be enrolled at dose level -1 such that safety is established in at least 6 patients prior to entering dose expansion phase.

Any delayed CNS-toxicity arising within the radiation field but seen beyond the window for DLT registration (> 8weeks following completion of FSRT) will be recorded. Furthermore, occurrence of any delayed-onset treatment related grade 3 or higher central nervous toxicity at any time (during and after DLT period of 8 weeks) will lead to holding dose-escalation and adding 3 patients to the dose level at which toxicity has occurred. Occurrence of additional delayed-onset treatment related grade 3 or higher CNS- toxicity will be reviewed with Protocol Monitoring Committee and IRB to determine whether discontinuation or modification of trial is subsequently warranted.

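### The delayed-onset CNS DLT stops at grade 4, so a related CNS death on days 31 to 56 after FSRT, not already logged as grade 3 or 4, is left out of the Table 2 counts

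*Combined protocol and SAP*

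**What the plan says.** All of the following is in Section 5.4 unless noted.

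- A DLT is a related event "occurring within 8 weeks from last dose of radiation therapy".
- Acute CNS DLT, up to 30 days after FSRT: "Any grade 3 or higher central nervous adverse events including but not limited to headache", followed by other examples.
- Delayed-onset CNS DLT, beyond 30 days: "Any grade 3 or 4 adverse event arising within the irradiated volume including but not limited to radiation necrosis or focal neurological deficits".
- "Dose escalation will be determined based on the occurrence of DLTs", counted by patient. Table 2 is indexed by the number of patients with a DLT. After 1 of 3, at least three more are entered. "If 1 or more of this group suffer DLT, then dose escalation is stopped".
- Hold rule after Table 2: "occurrence of any delayed-onset treatment related grade 3 or higher central nervous toxicity at any time", inside or after the 8 weeks, "will lead to holding dose-escalation and adding 3 patients to the dose level at which toxicity has occurred". A further such event goes to the Protocol Monitoring Committee and the IRB.
- Section 5.9 sets study-wide limits of 14% for neurologic death and 10% for symptomatic necrosis. It adds a sentence with no rate on delayed-onset toxicity of grade 3 or above, and speaks of closing the study.

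**The concern.** Two of the three CNS rules in Section 5.4 include grade 5; the delayed-onset DLT does not. Section 7.5 names grade 5 where it is meant, and nothing elsewhere adds it back. The general non-hematologic bullet does cover grade 5, but it sits under the non-CNS heading, and the section says that CNS and non-CNS toxicities are defined differently.

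A grade 4 in-field event on day 40 is therefore a DLT, while a fatal one first recorded at death is not. The hold rule reacts to the death but does not make it a DLT. The MTD and the recommended phase 2 dose rest on the Table 2 counts and belong to the primary endpoints, so the definition should not depend on how a death is interpreted after it has happened.

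**Working it through.** The documents state no figure to reproduce and give no rate for such deaths. All rates below are assumptions.

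**Timing.** FSRT runs on D1 to D5 (Section 10). The 8-week window ends 56 days after FSRT, so the gap is days 31 to 56, or 26 of 56 days (D36 to D61). With no dose delay, the final visit falls about 30 days after the D15 infusion, at D45, which is 40 days after FSRT. It is the only scheduled visit in the gap. The first follow-up MRI comes at about 3 months. A first record at death is therefore possible.

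**Inputs.** p = rate of ordinary DLTs (10, 20, 30%); f = rate of uncounted deaths (1, 2, 5%); n = 1 − p − f; cohorts of three.

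**If the death counts as a DLT:** P(escalate) = n³ + 3(p+f)n⁵.

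**As written, base reading.** One DLT or one death adds three patients, and any DLT among them stops escalation. A first death among the added three adds three more, who must have no DLT. A second death is treated as no escalation.

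- No event in the first three: n³.
- One DLT only: 3pn² × (n³ + 3fn² × n³).
- One death only: 3fn² × n³.
- One DLT and one death: 6pfn × n³.

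Subtracting the counted version leaves **6pfn⁴ + 9pfn⁷**. The first term is one DLT plus one death in the first three. The second is one DLT in the first three and a death among the added three. A lone death in the first three cancels, because the hold treats it like one DLT.

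Example, p = 20%, f = 2%, n = 0.78: 6 × 0.004 × 0.3702 + 9 × 0.004 × 0.1757 = 0.0089 + 0.0063 = 0.0152. The probabilities are 68.0% as written and 66.5% if counted.

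| f | p = 10% | p = 20% | p = 30% |
|---|---|---|---|
| 1% | +0.8 | +0.8 | +0.6 |
| 2% | +1.5 | +1.5 | +1.1 |
| 5% | +3.0 | +3.1 | +2.3 |

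(Percentage points, as written minus counted.)

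**After one DLT plus one such death in the first three, f = 2%.** Escalation needs an event-free addition.

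- Three patients added: n³ = 68%, 47%, 31% at p = 10, 20, 30%.
- Six added, if the Table 2 cohort and the hold cohort are separate: n⁶ = 46.4%, 22.5%, 9.9%.
- Death counted: 0%.

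That start has probability 6pfn = 1.1%, 1.9%, 2.4%.

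**Section 5.9 limits, all treated patients assumed as denominator.** 1/7 = 14.3% and 1/8 = 12.5%, so one neurologic death exceeds 14% up to 7 patients. 1/9 = 11.1% and 1/10 = 10%, so one fatal symptomatic necrosis exceeds 10% up to 9 patients.

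**Literal closure.** If Section 5.9 closes the study after one such event, it does so whether or not the event is a DLT. Any path with a death ends in both versions, and the difference is 0.

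**The case against.** The strongest reply is that the plan largely deals with the event elsewhere. The hold covers grade 5 and applies inside the window. The monitoring committee meets monthly and can suspend or close the study (Section 12.2). One death would exceed a Section 5.9 limit early in the trial. The trigger is also narrow: related, in-field, fatal, within 26 days and never logged at grade 3 or 4. Adverse event reporting is continuous (Section 7.4), so sparse visits do not show that the last condition would often be met. All of this stands, and it keeps the point minor. None of it makes the death a DLT, which is what Table 2 counts.

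Four stronger inferences are tempting and not supported:

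- *The death goes unnoticed and escalation simply continues.* The hold rule contradicts this.
- *The effect is 3 to 20 points.* Figures of that size come from Table 2 alone, with ordinary DLT rates of 10 to 33% and death rates of 2 to 10%. They leave out the hold.
- *A dose with a DLT and a death would be declared the recommended phase 2 dose at 1 of 6.* Table 2 does say of a level with at most 1 of 6 "This is the dose to be used in the expanded cohort and will be considered recommended phase 2 dose", but the hold would add three patients there first, and the plan does not say how they are scored.
- *The present wording is the stricter one if Section 5.9 closes the study.* That applies closure to only one side of the comparison. The edit leaves Section 5.9 unchanged.

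**Conclusion.** The definition is wrong as written, and the consequence is small. In the base reading the chance of escalating is 0.6 to 3.1 points too high over the assumed rates. It is 0 under literal closure. The clear failure is one DLT plus one such death in three patients: escalation remains possible where the count should stop it, but that start occurs in only about 1 to 2.4% of cohorts at f = 2%.

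The wording mismatch is certain. The size rests on assumed rates, on applying Table 2's expansion row to the hold, and on treating a second death as ending escalation. A more lenient outcome of committee review would widen the gap; action after the first death would narrow it. Severity: minor.

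**What to change.** In the delayed-onset CNS bullet of Section 5.4, replace the grade 3 or 4 range with grade 3 or higher. Add one sentence stating that such events within 8 weeks of the last radiation dose count as DLTs in Table 2, in addition to triggering the hold. The cost is a few words in an amendment, with no added patients or procedures.

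### The calendar schedules one blood count between D15 and the end of the DLT window at about D61, so a silent grade 4 cytopenia after the third dose can be missed and scored as no DLT

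*Combined protocol and SAP*

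**What the plan says.** - **DLT definition (section 5.4).** There are three hematologic criteria: "Grade 4 neutropenia lasting for" seven days or more; grade 3 or higher "febrile neutropenia with/without infection"; and "Grade 4 thrombocytopenia". Only the first carries a duration. All count when "occurring within 8 weeks from last dose of radiation therapy".
- **Treatment days.** Section 10, footnote a: "Radiotherapy will be delivered once daily Monday through Friday, D1-5 for a total of 5 treatments". Section 5.6 gives TPI 287 on D1, D8 and D15.
- **Blood schedule (section 10).** Footnote c: "Blood will include CBC and differential", plus chemistry. The blood row is marked at baseline, D1, D8, D15 and the final visit, and is blank for follow-up. Footnote f puts the final visit about 30 days after the last treatment.
- **Other text on counts.** Section 10 asks for repeat laboratory tests when a patient is deteriorating, in the 48 hours before a next cycle. Section 5.4 holds drug for grade 3 or 4 toxicity until recovery within 15 days. Section 6 ("Table 7. Management of Neutropenia", and Table 8 for platelets) takes a grade 4 patient off protocol therapy. Section 5.8 has treatment-related toxicities present at discontinuation followed until they resolve or stabilize. None of these gives a frequency for counts.

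**The concern.** Two of the three hematologic DLTs are laboratory findings that may cause no symptoms, so they are scored only if blood is drawn while they last. The D15 count is taken on the day of the third dose and cannot show that dose's later effect. Section 5.4 delays escalation for eight weeks to watch for late toxicity, yet the calendar puts one count into the part of that period after the third dose.

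Table 2 of section 5.4 escalates on counted DLTs, and an event nobody sees is counted as none. The error runs one way: a level can pass that would have been expanded or stopped, and the MTD can be set too high.

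**Working it through.** The documents state no error rate or operating characteristic on this point, so there is no figure of the plan's to reproduce.

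**1. Dates, assuming no delays**
- Last radiotherapy is D5, so the DLT window closes at 5 + 56 = D61.
- The last dose is D15, so the final visit is at about 15 + 30 = D45.
- Days without a scheduled count: D16-D44 (29 days) and D46-D61 (16 days). The 46 window days after dose 3 hold one scheduled count.
- The first follow-up contact (month 3 in section 5.7, or about 12 weeks after the final visit in footnote g) falls after D61 and has no blood marked.

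**2. Does an episode meet a scheduled count?** An episode of length L starting on day o occupies days o to o + L - 1. It is seen if D8, D15 or D45 falls in that run.

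| Onset days | L = 7 | L = 10 | L = 14 |
|---|---|---|---|
| D2-D15 (14 days) | 14 | 14 | 14 |
| D16-D29 (14 days) | 0 | 0 | 0 |
| D16-D44 (29 days) | 6 | 9 | 13 |

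For L = 7, the six onsets seen are D39-D44, which reach D45.

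**3. Can scheduled counts confirm seven days?** This needs two grade 4 counts at least seven days apart. For onsets on D16-D44 it happens for 0 of 29 at each of these lengths. For onsets on D2-D15, D8 and D15 bracket the episode for 0, 3 and 7 of 14 onsets at L = 7, 10 and 14.

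**4. Effect on escalation.** Table 2 passes a level with 0 of 3, or with 1 of 3 followed by 0 of 3. Ignoring its grade 2 CNS trigger, and with q = 1 - p:

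P(pass) = q³ + 3pq² × q³

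Assume 10% of patients have a DLT of another kind that is seen, and independently a further fraction u have a hematologic DLT that is not. The observed rate is p = 0.10, so P(pass) = 0.729 + 0.177 = 0.906. The true rate is p = 1 - 0.9(1 - u).

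| u (assumed) | True p | P(pass) as observed | P(pass) if seen |
|---|---|---|---|
| 4% | 0.136 | 0.91 | 0.84 |
| 10% | 0.19 | 0.91 | 0.73 |
| 20% | 0.28 | 0.91 | 0.54 |

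The 10% and every u are assumptions.

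**5. What added counts would do (L = 7, onsets D16-D44)**
- Adding D22 and D29: 7 + 7 + 6 = 20 of 29. Onsets on D30-D38 stay unseen.
- Adding D22, D29, D36 and D43: 29 of 29.
- Those four counts alone still confirm a duration of seven days for 0, 9 and 21 of 29 onsets at L = 7, 10 and 14, so a scoring rule is needed as well.

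**The case against.** A reader might infer that the hematologic DLTs cannot be observed at all, or that a seven-day duration can never be measured. The documents do not support either reading. Febrile neutropenia presents clinically, and adverse events are captured throughout participation (section 7.4). Thrombocytopenia needs a single count and can be seen on D8, D15 and about D45. Every episode of seven days or more starting on D2-D15 meets a scheduled count, and grade 4 values on both D8 and D15 bracket seven days. The hold rule and the follow-up requirement in section 5.8 also imply repeat counts once a toxicity is known.

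A reader might also take 0.54 as a realistic estimate. It is the severe end of an assumed range. In the prior weekly trial, neither neutropenia nor thrombocytopenia is among the related events at 10% or more (section 7.1.2), at any grade. That list pools dose levels, and section 7.1.2 names several overlapping terms for low counts, so it limits the likely rate without fixing it. Section 2.2 gives 24% neutropenia and 10% thrombocytopenia for single-agent experience, again without grade or timing. Finally, the top level, 127.5 mg/m², equals the single-agent weekly MTD, so missed events cannot take escalation above that dose. This does not show that the dose is tolerable with radiotherapy.

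These points narrow the concern but leave its core. The hold and follow-up provisions act only on a toxicity already found. The repeat-laboratory sentence is tied to a next cycle, and no dose follows D15 on the planned schedule. Open-ended questioning about adverse events (section 7.3) does not reveal a silent low count.

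**Conclusion.** Sections 5.4 and 10 do not match. Followed exactly, the calendar can miss asymptomatic grade 4 thrombocytopenia, or grade 4 neutropenia of seven days or more, that begins and recovers within D16-D44 or arises after the final visit. From scheduled counts alone, the duration of a neutropenia starting after dose 3 cannot be confirmed. The day counts rest on an undelayed schedule and a final visit at D45.

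The bias on the MTD is upward. Its size is unknown, because the documents give neither grade 4 rates nor nadir timing. The pass probabilities should be read as a range under assumed rates, not as an estimate.

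**What to change.** Reconcile sections 5.4, 5.8, 6 (Tables 7 and 8) and 10, so that the calendar can score the DLTs that the protocol defines:

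- Schedule blood counts between D15 and the final visit at intervals no longer than the seven-day criterion. State whether counts are also meant to cover the 16 window days after the final visit.
- State that patients taken off therapy for a grade 4 count keep having counts recorded until recovery, consistent with section 5.8. The hold rule in section 5.4 and the off-therapy entries in Tables 7 and 8 describe the same grade 4 patient differently and must be reconciled.
- State in section 5.4 how duration is scored when no count within seven days shows recovery. This convention helps only after a grade 4 count has been seen; it does not replace the added counts.

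The cost is amendment wording, about four routine draws per patient on a weekly schedule, and repeat draws after a grade 4 value. If missing recovery counts are scored as lasting seven days, some short neutropenias will be counted as DLTs.
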